8.4 Missed or Omitted Doses and Alternative Treatment Schedules

8.4.1 Missed Doses: RRx-001

If doses of RRx-001 doses are missed those doses will be skipped. If all the doses of RRx-001 are missed that patient may be considered non-evaluable. The missed or omitted dose(s) and the reason for omission should be recorded.

8.4.2 Missed or Omitted Doses: Cisplatin

In the event of any grade 3 or 4 event, treatment will be delayed. If the delay is more than 21 days because of hematologic or renal adverse events, that dose will be omitted. If a dose of cisplatin is missed or omitted, it will not be made up or added to the end of treatment. If radiotherapy is held, cisplatin should similarly be held and resumed when radiation resumes. In this case, the cisplatin dose is not considered skipped or omitted, but delayed.

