1 STUDY SCHEMA AND ASSESSMENTS

1.1 Treatment Schemas

1.2 Schedule of Assessments Table

Procedures	Screening	Pre-Treatment		Combination Treatment							Mucositis Observation Follow-up	28 Day Post IMRT Safety Visit ¹⁷	Long-Term Follow-Up ¹⁸				
		Wk -2	Wk -1	Wk 1	Wk 2	Wk 3	Wk 4	Wk 5	Wk 6	Wk 7 ¹⁶	weekly (until OM grade ≤ 1)		3 mo post RT	6 mo post RT	9 mo post RT	12 mo post RT	
	≤ 28 Days of Tx Start	D1 ±2d	D8 ±2d	D15 ±2d	D22 ±2d	D29 ±2d	D36 ±2d	D43 ±2d	D50 ±2d	D57 ±2d	following end of IMRT	28 days post end of IMRT +5 days	± 7 days	± 14 days	± 14 days	± 14 days	
Informed Consent	X																
Demographics	X																
Medical & Onc History ¹	X																
Dental Assessment ²	X																
Laryngopharyngoscopy ³	X										X	X	X	X	X	X	X
Audiogram ⁴	X																
Physical Exam ⁵	X	X	X	X	X	X	X	X	X	X	X	X	X				
Oral Mucositis Assessment (WHO, CTCAE) ⁶	X	X		X	X	X	X	X	X	X	X	X	X				
Oral Mucositis Daily Questionnaire (OMDQ) ⁷	X			X	X	X	X	X	X	X	X	X	X				
Oral Routine Assessment ⁸			X														
Vital Signs	X	X	X	X	X	X	X	X	X	X							
ECOG Status	X	X	X	X	X	X	X	X	X	X	X	X	X				
Lab Assessments ⁹	X	X	X	X	X	X	X	X	X	X		X					
Pregnancy Test ¹⁰	X																
Adverse Events		X	X	X	X	X	X	X	X	X	X	X	X				
Concomitant Medications & Procedures	X	X	X	X	X	X	X	X	X	X	X	X	X	X	X	X	X
Chest CT or PET/CT ¹¹	X													X ¹¹			
CT, MRI, or PET/CT of tumor site & neck nodes ¹²	X													X ¹²			
RRx-001 Administration ¹³				X ¹³													
Cisplatin Administration ¹⁴				X	X	X	X	X	X	X							
Radiation Therapy (IMRT) ¹⁵				X	X	X	X	X	X	X							

Schedule of Assessments Table Footnotes

1. Record patient cancer and medical history as well as previous oral history (i.e. previous occurrences of oral mucositis, history of smoking, alcohol consumption, dry mouth (xerostomia), chewing tobacco usage, and dental history).
2. Dental Assessment: ENT examination recommended during screening to perform dental assessment.
3. Laryngopharyngoscopy: mirror (indirect laryngopharyngoscopy) and/or fiberoptic (direct laryngopharyngoscopy) procedure is recommended at these time points but is not required (at discretion of treating physician).
4. Audiogram: Recommended within 84 days of starting treatment but is not required.
5. Physical Exams:
 - A *full* physical exam must be performed during screening (including: ECOG status, swallowing assessment and assessment for PEG Tube), and during Combination Treatment week 1 and at the 28 Day Safety Visit (post treatment).

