--	---

Statistical Methods
	
Safety Endpoints:
 
 • Incidence of adverse events, including serious adverse events (SAEs) and clinically significant laboratory abnormalities. • Overall tumor response to treatment using RECIST or site preference criteria. 
Efficacy Endpoints:
 
 • Duration (in days) of severe oral mucositis (SOM, WHO grades 3 or 4) • Time (in days) to onset of SOM • Incidence of SOM • Incidence and duration of ulcerative mucositis (WHO grades 2, 3, 4) • Patient-reported mucositis pain as measured by question 2 of the Oral Mucositis Daily Questionnaire 
Design:
 
This is a randomized, open-label, parallel group, Phase 2 study to assess the safety and radioprotective potential of RRx-001 in patients undergoing chemoradiation therapy for locally advanced head and neck cancer.
 
A total of approximately 40 patients will participate in this study. All patients will receive standard chemoradiation therapy consisting of cisplatin either every three weeks (100 mg/m² for 3 doses) or weekly (40 mg/m² for 7 doses) + radiotherapy (IMRT) administered daily (except weekends) for 7 weeks. In conjunction with this “standard of care” (SOC), patients will be randomly assigned to receive one of 3 regimens of RRx-001 or a control (no treatment).
 
Sample Size:
 
A sample size of approximately 40 patients (~10 per group) is considered adequate for this proof-of-concept (POC) study to explore the radioprotective potential of RRx-001 and identify a safe regimen for further development.
 
Statistical Methods:
 
Efficacy and safety data will be summarized using descriptive statistics, including the mean, standard deviations, median, minimum and maximum for continuous endpoints and frequency tables for categorical data.
 
Efficacy Analysis:
 
Hypothesis testing of efficacy endpoints will be performed for exploratory purposes only. For continuous efficacy endpoints, non-parametric methods will be used to compare each RRx-001 group to the untreated control group (Wilcoxon rank-sum tests). Fisher’s exact test will be used to evaluate treatment differences for binary outcomes. Two-sided 95% confidence intervals will be calculated for proportions using the Clopper-Pearson method.
 
Safety Analysis:
 
Safety data, including adverse events (AEs), serious adverse events (SAEs), ECOG performance status, clinical laboratory tests, vital signs and physical examination results will be listed and summarized descriptively by treatment group. Adverse events will be coded by system organ class (SOC) and preferred term using MedDRA (Version 18.1), and severity will be based on NCI CTCAE Grade criterion (Version 5.0).
 
Descriptive statistics (sample size, mean, median, standard deviation, quartiles and range) and graphical methods (longitudinal plots) will be used to present change from pre-treatment values in laboratory parameters during the treatment period. The incidence of febrile neutropenia, bacterial infections, grade 3 or 4 cervicofacial dermatitis, and other toxicities of clinical interest (xerostomia, trismus, fatigue, weight loss, radiation dermatitis, and dysgeusia) will be tabulated by treatment arm.

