8.3.2 Dosing Delays/Dosing Modifications: Cisplatin

- **Neutropenia:** If on the day of scheduled treatment with cisplatin the absolute neutrophil count (ANC) is < 1200 , hold treatment until $ANC \geq 1200$, then treat at 100% dose. Neutropenic fever will require permanent 25% dose reduction. Per CTCAE, v. 5.0, febrile neutropenia is described as $ANC < 1000/mm^3$ with a single temperature of > 38.3 degrees C (101 degrees F) or a sustained temperature of ≥ 38 degrees C (100.4 degrees F) for more than 1 hour.
- **Thrombocytopenia:** If on the day of scheduled treatment with cisplatin the platelet count is $< 75,000$, hold treatment until platelets are $\geq 75,000$, then treat at 100% dose. Thrombocytopenia that results in bleeding will require a 25% dose reduction
- **Neurotoxicity:** If any signs of grade 3 or greater neurotoxicity occur, discontinue cisplatin. Continue radiation therapy (RT).
- **Renal Adverse Events:** Cisplatin should be administered on the scheduled day of treatment using the following guidelines. Note: If creatinine is > 1.2 mg/dL, clearance must be calculated (Cockcroft-Gault) in order to make dose adjustment. If the calculated nomogram is 50 mL/min or above, a 24-hour urine collection is not needed, but if the calculation is less than 50 mL/min, a 24-hour urine collection is mandated.

Creatinine Clearance	Cisplatin Dose 100 mg/m ²	Cisplatin Dose 40 mg/m ²
> 50 mL/min	100 mg/m ²	40 mg/m ²
40-50 mL/min	50 mg/m ²	20 mg/m ²
< 40 mL/min	Hold drug*	Hold drug*

*Cisplatin should be held (but RT continued), and the creatinine measured weekly. If creatinine clearance is > 50 mL/min, then the second dose of cisplatin can be given at the reduced dose of 50 mg/m² or 20 mg/m². Also see [Section 8.4.2](#) below.

- *Other Adverse Events*
 - **Mucositis:** Significant mucositis from radiation and cisplatin is expected and will not be an indication for cisplatin dose modification. No cisplatin dose reductions will be made.
 - **Ototoxicity:** For new clinical hearing loss not requiring a hearing aid or for tinnitus that interferes with activities of daily living, treat at 50% dose reduction. For hearing loss requiring a hearing aid, discontinue cisplatin. Continue RT and RRx-001. If the physician is unsure about the severity of the hearing loss, an audiogram is encouraged.

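### Sections 8.3.2 and 8.4.2 do not settle whether grade 3-4 oral mucositis delays cisplatin, so cisplatin timing may depend on the trial's own endpoint

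*Combined protocol and SAP*

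**What the plan says.** Two cisplatin sections bear on the same event.

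- **Section 8.4.2** (missed or omitted cisplatin doses): "In the event of any grade 3 or 4 event, treatment will be delayed". It goes on: "If the delay is more than 21 days because of hematologic or renal adverse events, that dose will be omitted", and "If a dose of cisplatin is missed or omitted, it will not be made up or added to the end of treatment".
- **Section 8.3.2**, headed "Dosing Delays/Dosing Modifications: Cisplatin": "Significant mucositis from radiation and cisplatin is expected and will not be an indication for cisplatin dose modification". The next sentence is "No cisplatin dose reductions will be made".

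The event in question is the efficacy endpoint. The study summary lists "Duration (in days) of severe oral mucositis (SOM, WHO grades 3 or 4") first among the efficacy endpoints. The schedule of assessments grades mucositis on two scales: "Oral Mucositis Assessment (WHO, CTCAE"). Section 8.4.2 does not say which scale its grades refer to.

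Section 13 plans no by-arm summary of cisplatin delays, omissions or cumulative dose. Section 11.4 records interruptions of radiation only. The instruction to record missed doses with the reason is in section 8.4.1, which concerns RRx-001.

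**The concern.** Read literally, the trigger in 8.4.2 includes severe mucositis, while 8.3.2 sets mucositis aside as a reason to modify the dose. A site holding cisplatin for a patient with grade 3 mucositis and a site giving it on schedule could each cite the protocol.

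The stake is that a post-randomisation co-treatment may be driven by the outcome. Section 3.1 says that concomitant chemotherapy raises the risk and severity of mucositis, and that treatment breaks for mucositis may cost survival. If RRx-001 reduces SOM and sites delay for SOM, controls would have more delays. That could shrink the SOM difference. It could also confound tumour response (a stated objective) and progression-free survival (section 13.3): less timely cisplatin in controls could hide a tumour-protective effect of RRx-001. The trial is open label, so an unclear rule can also be applied differently by arm. With no planned cisplatin summary, none of this would be visible in the results.

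**Working it through.** **1. The two sections side by side**

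| Question | 8.3.2 | 8.4.2 |
|---|---|---|
| Is mucositis a trigger? | No, for dose modification | Not mentioned; any grade 3 or 4 event |
| Action addressed | Modification, then reductions | Delay |
| Grading scale | None named | None named |
| Fate of a dose delayed for mucositis | Not stated | Not stated; the 21-day omission rule covers hematologic or renal causes only |
| Which section governs? | Refers to 8.4.2 only in the renal footnote | Not stated |

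The first sentence of 8.4.2 is not naturally limited to hematologic or renal events, because the next sentence adds that limit for omission and the first does not. The same first sentence also sits badly with 8.3.2 on neurotoxicity, where grade 3 or worse leads to discontinuation and not delay.

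**2. The plan's own figure**

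Inputs from section 13.1: mean SOM 24 v 6 days, SD 13, two-sided 5%, Student's t-test, 10 per group. The effect size is 18/13 = 1.385. The t-test needs n = 9.25 per group for 80% power, rounded up to 10, so the stated size reproduces. Power at n = 10 is 83.3%.

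**3. How often the conflict would arise**

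Section 13.2 assigns 0 days to patients without SOM. If a mean of 24 and SD of 13 describe controls on that definition, the share with any SOM is at least (mean)²/[(mean)² + SD²] = 576/(576 + 169) = 77% (Cauchy-Schwarz bound). This is relevant only so far as the grade in 8.4.2 coincides with the WHO grade.

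**4. Scheduled doses falling inside an SOM episode**

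Inputs:
- Section 8.2, counted from the first day of radiotherapy: weekly doses fall on days 1, 8, 15, 22, 29, 36 and 43, and three-weekly doses on days 1, 22 and 43.
- Section 3.1: ulceration starts at 20 to 30 Gy (end of weeks 2 to 3 at 10 Gy a week) and peaks at the end of week 5.

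Assumptions: one unbroken episode of exactly the arm-mean length, onset on any day from 15 to 43, and planned dose days unchanged. A dose counts if onset ≤ dose day < onset + duration.

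| Onset day | Weekly, 24 d | Weekly, 6 d | Three-weekly, 24 d | Three-weekly, 6 d |
|---|---|---|---|---|
| 15 | 4 | 1 | 1 | 0 |
| 16 | 3 | 0 | 1 | 0 |
| 22 | 4 | 1 | 2 | 1 |
| 29 | 3 | 1 | 1 | 0 |
| 36 | 2 | 1 | 1 | 0 |
| 43 | 1 | 1 | 1 | 1 |
| **Range, all days 15-43** | **1-4 of 7** | **0-1 of 7** | **1-2 of 3** | **0-1 of 3** |

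As shares of the planned course, the weekly figures are 14% to 57% v 0% to 14%, and the three-weekly figures 33% to 67% v 0% to 33%. The gap between arms at a given onset day is 0 to 3 weekly doses or 0 to 1 three-weekly dose. It is zero for onset from day 38 on, and zero at any onset if SOM duration is the same in both arms.

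**5. What dilution would do to power**

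The documents give no figure for how far delays would shorten SOM, so these values are assumed. If control SOM fell from 24 to 20 days with the active arm still at 6, t-test power at n = 10 would fall from 83% to 62%. At 18 days it would be 50%.

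**The case against.** **This is ambiguity and not contradiction.** The heading of 8.3.2 lists delays and modifications as separate things. Its mucositis bullet goes on to mention only reductions, whereas the neutropenia and thrombocytopenia bullets speak of holding treatment. Delay at full dose is compatible with both texts. Alternatively, the specific mucositis bullet may govern the general sentence. This stands as far as calling the two sections flatly contradictory is concerned. It does not settle the matter, because it shows two defensible readings with different consequences for dosing.

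**The arms need not differ.** A reader might infer that cisplatin exposure will differ by arm. The documents do not show that. Patients are randomised, and a difference needs either an RRx-001 effect on SOM or unequal application by unblinded staff.

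**Controls need not receive less cisplatin.** Section 8.4.2 prescribes delay. Omission is specified only for hematologic or renal causes. Timing changes directly; a change in cumulative dose is an inference, as is the idea that delaying a dose shortens an episode already under way.

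**Simple division overstates precision.** Dividing 24 and 6 days by 7 suggests that 3.4 v 0.9 of 7 weekly doses (49% v 12%) fall within SOM. That takes the whole episode to lie inside the dosing period, although lesions typically heal 2 to 4 weeks after radiotherapy and follow-up assessments count towards duration. The range in the working is the supportable statement.

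**Which treatment is meant is clear enough.** The heading and the following sentences of 8.4.2 make it cisplatin.

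**Some variation is accepted by design.** Section 8.2 defers to institutional guidelines, and all analyses are exploratory. This lowers the stakes, but it makes a by-arm record of cisplatin more useful.

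**Conclusion.** The point holds as an unresolved internal conflict on the trial's own endpoint event. The documents do not say whether grade 3-4 oral mucositis delays cisplatin, on which scale, which section governs, or what happens to a dose so delayed.

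If 8.4.2 is applied to SOM, cisplatin timing depends on the endpoint. Under the plan's 24 v 6 days and the assumptions stated in the working, the arm gap in doses falling due during SOM is 0 to 3 of 7 weekly doses or 0 to 1 of 3 three-weekly doses. With no RRx-001 effect on SOM and equal application of the rule, the expected gap is zero. Dilution of the SOM comparison and confounding of tumour response and progression-free survival are possible consequences whose size the documents do not allow one to estimate. The sponsor should correct this, but it does not by itself invalidate the design.

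**What to change.** 1. Reconcile sections 8.3.2 and 8.4.2 in a single statement that says whether grade 3-4 oral mucositis falls under the 8.4.2 trigger, on which scale (WHO or CTCAE), whether a delay counts as a modification, and what becomes of a dose delayed for mucositis. The neurotoxicity wording should be reconciled at the same time. The choice of clinical rule is for the investigators.
2. State that cisplatin delays and omissions are recorded with dates and reasons. The documents do not show that this is already captured for cisplatin.
3. Add to section 13 a table by arm of cisplatin delays, omissions and cumulative dose, with reasons, to be read alongside the SOM, tumour response and progression-free survival results.

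The cost is one protocol clarification, a small addition to data capture and one exposure table. Sample size and the planned tests do not change.

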9 RADIATION THERAPY

Intensity Modulated Radiation Therapy (IMRT) in accordance with the American College of Radiology (ACR) and American Society for Radiation Oncology (ASTRO) Practice Guideline for IMRT) is mandatory for this study [[Hartford 2012](#)].

10 OTHER THERAPY

10.1 Permitted Concomitant Supportive Therapy

Patients should receive full supportive care while on this study. This includes blood product support, antibiotic treatment, antifungal treatment, and treatment of other newly diagnosed or concurrent medical conditions. All supportive care should be listed as a concomitant medication.

Patients will conform to a standard oral care regimen consistent with national/international guidelines and will be provided instructions and supplies to assure adherence ([Appendix F](#) & [Appendix G](#)).

10.2 Non-permitted Concomitant Supportive Therapy

- Amifostine
- Topical antibiotic rinses, creams or troches
- Benzydamine hydrochloride
- Caphosol
- Glutamine (topically applied)
- GM-CSF (Leukine)
- IL-11
- Magic mouthwash or Miracle mouthwashes are allowed as long they do not contain any of the following:

- Chlorhexidine
- Diphenhydramine
- Tetracycline or other antibiotic
- Hydrogen peroxide
- Other disallowed medications:
 - Herbal, alternative remedies, other natural product (i.e. honey) and alcohol-containing mouthrinses.
 - MuGard
 - GelClair
 - Episil
 - Prothelial
 - Palifermin or other growth factors
 - Povidone-iodine rinses
 - Prevention mouth rinse
 - ReBalance
 - Steroid rinses or gels
 - Sucralfate suspension for topical use (oral formulations, i.e., tablets are allowed).
 - Other biologic modifiers. Hematopoietic growth factors such as GCSF are allowed.
 - Other investigational agents.

If non-permitted concomitant supportive therapies are used ([Section 10.2](#)) the data may be censored and the patient may be replaced.

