To date, palifermin (KGF1), a pleiotropic growth factor, is the only agent approved for mucositis and its use is limited to patients receiving stomatotoxic conditioning regimens prior to hematologic stem cell transplant. Despite an active developmental pipeline of compounds to prevent and/or treat OM, which includes dusquetide, an immunomodulatory peptide, GC4419, a dismutase mimetic, brilacidin, a defensin mimetic, current treatment options are mainly limited to topical barrier devices for symptom management, opioid and NSAID analgesics, ice chips (cryotherapy) and oral rinses such as “magic mouthwashes” that vary in composition depending on institutional folklore. None of these approaches has adequately mitigated the clinical development of mucositis or its symptoms. Thus, the degree of the unmet need in mucositis is related to the severity of symptoms and the lack of an approved treatment regimen, which, if addressed, would substantially improve quality of life and treatment outcomes for head & neck cancer patients.

The rationale for this trial is that RRx-001, as a systemically non-toxic putative dual radiochemoprotector/sensitizer with activity in multiple tumors types including small cell carcinoma of the oral cavity, will protect the normal mucosa but not the tumor and delay the duration of oral toxicity.

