11.3 Analgesic Use

Patients often require analgesics, including opioids for pain control. Patients will record any analgesic use, including name, dose, and frequency of dose, in the OMDQ Booklet. Information from the source documents and the diary will be recorded into the EDC system as a concomitant medication. Analgesics will be converted to morphine equivalents at the time of data analysis.

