13.2 Efficacy Analysis

Statistical methods for the calculation and analysis of efficacy endpoints are provided below. Limited hypothesis-testing will be performed, as this is a small POC study. All statistical analyses are exploratory.

Duration of Severe Oral Mucositis (SOM): The duration of SOM (WHO grade 3 or 4) will be calculated as the number of days from the onset of SOM (first time a WHO grade 3 or 4 is observed) to the day when severe OM has resolved (first time WHO grade 2 or less is observed after last WHO grade 3 or 4). Durations of 0 will be assigned to patients who do not experience severe OM. Any patient who dies or withdraws prior to resolution of severe OM will be assumed to have severe OM for the remainder of the observation period. All available OM assessments will be used to derive efficacy endpoints, including WHO grades recorded during the treatment and follow-up period in order to capture resolution of OM.

The duration of SOM will be compared for each of the 3 RRx-001 regimens versus the untreated control group using the Wilcoxon rank-sum test. This rank-based test does not depend on normality assumptions for these small sample sizes. All patients randomized (the intent-to-treat population) will be used for this analysis.

Time to onset of SOM: The number of days from the start of chemotherapy until the date of first OM assessment grade 3 or 4 will be listed and summarized descriptively for each treatment group.

Incidence of SOM: The incidence of SOM (WHO grade 3 or 4) will be calculated as the number of patients with at least one OM WHO grade 3 or 4, divided by the number patients in the treatment group. Patients with no OM assessments will be assumed to have severe scores. Patients who die or withdraw without experiencing OM grade 3 or 4 will also be assumed to have severe scores. The incidence of SOM will be compared between each RRx-001 group and the control arm using Fisher's Exact test. Clopper-Pearson two-sided 95% confidence limits will be calculated for the proportion of patients with SOM in each treatment arm.

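### Section 10.2 allows discretionary censoring and replacement after non-permitted product use, which conflicts with the all-randomised, all-assessments analysis in Section 13.2; the direction of any resulting bias is unknown

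*Combined protocol and SAP*

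**What the plan says.** Section 10.2 lists products that patients may not use. It ends by saying that if one is used, "the data may be censored and the patient may be replaced". The trigger is therefore defined. What is left open is when the option is exercised, which data are censored and from what date, who decides and whether that person knows the arm, and whether a replaced patient stays in the analysis.

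Section 13.2 is written in mandatory terms:

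- On the population for SOM duration: "All patients randomized (the intent-to-treat population) will be used for this analysis".
- On the data: "All available OM assessments will be used to derive efficacy endpoints".
- On incomplete follow-up for duration: "Any patient who dies or withdraws prior to resolution of severe OM will be assumed to have severe OM", for the rest of the observation period.

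The other imputation rules in Section 13.2 cover death, withdrawal and patients without any OM assessment. None mentions product use or replaced patients. The only censoring rule in Section 13 is the one for progression-free survival in Section 13.3. The words evaluable (Section 2) and non-evaluable (Section 8.4.1) appear, but neither is defined for analysis.

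Section 13.2 also states: "All statistical analyses are exploratory".

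**The concern.** OM data that have been censored are not all the available OM data, so Section 10.2 permits something that Section 13.2 rules out. Replacement alone is compatible with intent-to-treat if the original patient is kept, but the protocol does not say so. Two analysts could each follow the document and report different results.

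Three features make the gap worth closing:

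- **Link to outcome.** Section 3.1 says "current treatment options are mainly limited to topical barrier devices for symptom management, opioid and NSAID analgesics, ice chips (cryotherapy) and oral rinses". Several listed products are rinses, gels or barrier products of that kind, so their use may follow worse mucositis. This is an inference; the documents give no usage rate.
- **Knowledge of arm.** The trial is open-label (Section 6.1). Central WHO scoring (Section 1.2, footnote 6) protects the grade, but it does not govern whose data are set aside.
- **Size.** With about 10 patients per arm, one or two post-randomisation decisions can move an arm's mean by days.

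What is at stake is the reading of efficacy trends that Section 13.1 says will inform future study designs. No confirmatory claim depends on it.

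**Working it through.** **1. The plan's own figure.** Section 13.1 gives 10 per group, 24 versus 6 days, SD 13, two-sided 5%, t-test. The noncentrality is 18 / (13 × √(2/10)) = 18 / 5.81 = 3.10. Exact power is 83.3% with 10 per group and 78.7% with 9, so 10 is the smallest size that reaches 80%. The sample size is not in dispute.

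**2. Model for the illustration.** Control durations have mean 24 and SD 13 (Section 13.1), with zero for patients without SOM (Section 13.2). The documents do not give the proportion with SOM, P(SOM). The mean and SD force it to be at least 24² / (24² + 13²) = 576/745 = 0.77. I assume 0.85, so the mean duration among patients with SOM is 24/0.85 = 28.2 days. Durations among those patients are taken as gamma. The test is the two-sided 5% Wilcoxon, 10 versus 10. With no drug effect and everyone kept, false positives favouring RRx-001 are 2.2%.

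**3. One or two SOM patients (k) in one RRx-001 arm have OM data cut at product use; no drug effect.** Section 13.2 does not say how such a duration would be completed, and the two obvious readings give opposite signs.

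*(a) The cut duration is taken as completed, with the cut halfway.* Spurious benefit = k × 28.2 × 0.5 / 10:

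- k = 1: 1.4 days, false positives 3.9%
- k = 2: 2.8 days, false positives 6.8%

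*(b) Severe OM is assumed for the rest of observation.* This follows by analogy with the death and withdrawal rule. The final duration T is an assumption, 45 to 60 days. Spurious harm = k × (T − 28.2) / 10:

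- k = 1: (45 − 28.2)/10 = 1.7 to (60 − 28.2)/10 = 3.2 days
- k = 2: 2 × 16.8/10 = 3.4 to 2 × 31.8/10 = 6.4 days
- False positives favouring RRx-001 fall below 0.6%

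On the choice of T: seven weeks of radiation plus the six weeks of OM follow-up in Section 6.1 make 49 + 42 = 91 days. SOM beginning on day 31 to 46 would then last 60 to 45 days.

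**4. The same patients removed, chosen at random.** Spurious benefit = 24 − 28.2 × (8.5 − k)/(10 − k), which gives 0.5 or 1.1 days; false positives are 2.6% or 3.1%. Removing the longest durations from one arm gives 2.0 or 3.8 days and 5.4% or 9.6%. That is an upper bound only.

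**5. The rule applied alike in both arms.** Removal creates no false benefit when the drug has no effect. Under a true 24 versus 6 days (treated P(SOM) assumed 0.30; power 80% with all kept), applying the rule to a random 20% of SOM patients in each arm gives:

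- Removal without replacement: effect about 18 days, power 75%
- Cut halfway, taken as completed: effect 16.2 days, power 80%

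**The case against.** The best defence is that the conflict is more apparent than real. Section 13.2 is the analysis section and says what will be done; Section 10.2 is a concomitant-therapy section and says what may be done. On a fair reading Section 13.2 prevails and already keeps product users with all their grades. This largely stands: a reader might infer that the plan has no rule for these patients, and the mandatory wording of Section 13.2 does not support that. What remains is that Section 10.2 does not label its censoring as supplementary, no text gives either section precedence, and the all-randomised sentence is attached only to SOM duration.

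A second tempting inference is that the permission would favour RRx-001. The documents do not support this either. It requires a cut duration to be read as completed, whereas the nearest rule in Section 13.2 assumes severe OM continues, and that reverses the sign within the same arm. That rule names only death and withdrawal, so it applies by analogy at most. Neither reading is established.

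Third, no differential use between arms is documented, and patients have permitted options. Section 11.3 notes "Patients often require analgesics, including opioids for pain control", and Section 10.2 says "Magic mouthwash or Miracle mouthwashes are allowed as long they do not contain any of the following" before naming the barred ingredients. Random removal of one or two patients has a small effect. These points stand, and they limit the size of the problem.

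Finally, Section 13.1 speaks of identifying a safe regimen, and no efficacy rule for choosing a regimen is stated. That also stands.

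**Conclusion.** The inconsistency is real. Section 10.2 permits unblinded, discretionary changes to post-randomisation OM data that Section 13.2 says will be used in full, and nothing reconciles them.

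If the permission were used for one or two patients in a single RRx-001 arm, the mean difference in SOM duration could shift by roughly 1 to 6 days under the two censoring readings, against a planned difference of 18. The shift could go either way. This rests on an assumed P(SOM) of 0.85, gamma durations, a halfway cut or a final duration of 45 to 60 days, and an assumed count of affected patients.

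It would go too far to conclude that the trial's results will be biased. The permission may never be used, and even-handed removal creates no false benefit under the null. With every analysis labelled exploratory, I rate this minor to should-fix.

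**What to change.** Amend the last sentence of Section 10.2 so that Section 13.2 governs:

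- Use of a listed product is recorded as a protocol deviation.
- The patient, whether or not replaced, stays in OM assessment and in the intent-to-treat analysis with all observed WHO grades.
- Any analysis that censors or excludes product users is supplementary, with the exclusions fixed blind to arm before OM data are tabulated.

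The sponsor may keep the replacement option on these terms. Add one cross-reference in Section 13.2 that applies the rule to all OM endpoints, since the all-randomised sentence now covers only SOM duration.

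The cost is one amended passage and one added line, with no change to the product list and no extra assessments. The downside is that the intent-to-treat estimate will include any effect of the non-permitted products. That effect cannot be sized because the documents give no usage rate, but it follows from the analysis that Section 13.2 already specifies.
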